### **15.1.1 All Adverse Events**

All AEs recorded during the course of the trial (ie, assessed from signature of informed consent until the end of the Follow-up/End of Trial visit) will be coded according to MedDRA latest version and assigned to a SOC and PT.

TEAEs will be summarized by worst severity, using MedDRA latest version preferred term as event category and MedDRA primary system organ class (SOC) body term as Body System category. The severity of AEs will be graded using the “National Cancer Institute - Common Terminology Criteria for Adverse Events” (NCI-CTCAE) guideline, as detailed in the study protocol.

TEAEs related to trial treatment are those events with relationship missing, unknown or related.

The following will be summarized in an overview table with the number and percentage of subjects (and the number of events) by treatment and overall:

- Any TEAE
- Any trial treatment related TEAEs
- Any TEAE related to omeprazole
- Any TEAE related to tepotinib
- Any serious TEAEs

- Any trial treatment related serious TEAEs
- Any omeprazol related serious TEAEs
- Any tepotinib related serious TEAEs
- Any severe TEAE (grade  $\geq 3$ )
- Any trial treatment related severe TEAE (grade  $\geq 3$ )
- Any omeprazol related severe TEAE (grade  $\geq 3$ )
- Any tepotinib related severe TEAE (grade  $\geq 3$ )
- Any TEAEs leading to death
- Any trial treatment related TEAEs leading to death
- Any omeprazole related TEAEs leading to death
- Any tepotinib related TEAEs leading to death

TEAEs will be summarized by treatment and overall in tables with:

- The number and percentage of subjects by treatment with at least one TEAE and the number of events overall and by SOC and PT. Group/SOC terms will be sorted alphabetically and PTs within each group/SOC term will be sorted by descending frequency.
- The number and percentage of subjects by treatment with at least one non-serious TEAE and the number of non-serious TEAE applying frequency threshold of 5%. Group/SOC terms will be sorted alphabetically and PTs within each group/SOC term will be sorted by descending frequency.

In addition the following tables will be provided. Group/SOC terms will be sorted alphabetically and PTs within each group/SOC term will be sorted by descending frequency (based on all treatment groups combined):

- A table by severity of TEAEs with the number and percentage of subjects by treatment with at least one TEAE and the number of events by SOC and PT.
- A table by relationship to trial treatment with the number and percentage of subjects by treatment with at least one TEAE and the number of events by SOC and PT.

Pre-treatment AEs (AEs with onset after informed consent but before start of treatment) and TEAEs will be listed separately.

### **15.1.2 Adverse Events Leading to Treatment Discontinuation**

TEAEs leading to permanent discontinuation of trial treatment will be summarized by treatment and overall including number of subjects, percentage and number of events.

A listing of TEAEs leading to permanent discontinuation of a trial treatment will additionally be provided.

## **15.2 Deaths, Other Serious Adverse Events, and Other Significant Adverse Events**

### **15.2.1 Deaths**

All deaths as well as reason for death will be based on information from the “Report of Subject Death” eCRFs.

Listing of deaths, if any, will be provided displaying date and cause of death (including TEAE leading to death and relatedness to trial treatment, when applicable), and date and time of treatment administration.

### **15.2.2 Serious Adverse Events**

A summary table of SAEs, if any, by treatment and overall will be provided displaying the number and percentage of subjects by treatment with at least one SAE and the number of SAE overall and by system organ class and preferred term. Group/SOC terms and PTs within each group/SOC term will be sorted alphabetically.

Listing of SAEs, if any, will be provided in addition.

### **15.2.3 Other Significant Adverse Event**

#### **15.2.3.1 Adverse Events of Special Interest**

Healthy subjects might experience asymptomatic elevations in serum lipase and amylase. Any elevation in serum lipase and amylase of Grade  $\geq 3$  will lead to the recording of an adverse event of special interest (AESI). The severity of these AEs should be defined based on clinical judgment of the Investigator and defined according to NCI-CTCAE Severity Scale.

Adverse events of special interest will be presented in a separate data listing.

## **15.3 Clinical Laboratory Evaluation**

All laboratory data will be reported with SI units. Laboratory parameters will be listed by subject and time-point and summarized indicating the treatment at the respective time-point using descriptive statistics for absolute values and change from baseline over time.. Data listings of abnormalities as per the NCI-CTCAE guideline will be provided. Shift tables for laboratory tests will be presented by treatment. Shift tables will be based on NCI-CTCAE grades, where possible, and on normal ranges otherwise. They will be produced for

- End of Trial versus Screening
- Discharge versus Pre-dose (Tepotinib administration) within periods.

Laboratory values that are outside the normal range will also be flagged in the data listings, along with corresponding normal ranges and NCI-CTCAE grade and will additionally be listed separately.

See section 7.4.3 of the clinical study protocol for a table of the safety laboratory evaluations.

Safety laboratory values are separated into:

- Hematology
- Biochemistry
- Urinalysis
- Other tests

## 15.4                    **Vital Signs**

Vital signs will be listed by subject and time-point and summarized for absolute values and changes-from-baseline by visit and treatment using descriptive statistics. Descriptive statistics tables will start at baseline.

## 15.5                    **ECG Evaluation**

ECG data will be listed by subject and time-point and summarized by absolute values and changes-from-baseline by treatment group using descriptive statistics. Descriptive statistics tables will start at baseline. Clinically significant ECG findings for individual subjects will be listed and summarized.

The time intervals [PR, QRS, RR, QT and corrected QT intervals [based on Fridericia's formula, QTcF] will be summarized descriptively by treatment.

The Fridericia's Correction (QTcF) is derived as follows:

$$\text{Fridericia's Correction (QTcF)} \quad QTc_f = \frac{QT}{\sqrt[3]{RR}}$$

where: RR = RR-interval measured in seconds.

Observed QTcF values will be categorized according to their absolute values into the categories

- $\leq 430$  ms,
- $> 430$  and  $\leq 450$  ms,
- $> 450$  and  $\leq 480$  ms,
- $> 480$  and  $\leq 500$  ms, and
- $> 500$  ms,

and categorized according to their absolute change from baseline into the categories

- $\leq 30$  ms,
- $> 30$  and  $\leq 60$  ms, and
- $> 60$  ms.

The number and percentage of subjects by these categories at any post-dose assessment will be tabulated by treatment group. All ECG measurements will be listed, with abnormalities indicated.

Investigator reported interpretation results will also be listed and tabulated treatment using the number and percentage of subjects for each interpretation category (Normal, Abnormal Not Clinically Significant [NCS], Abnormal Clinically Significant [CS].

## **16 Analyses of Other Endpoints**

### **16.1 Pharmacokinetics**

#### **General Specifications for Plasma Concentration Data**

PK concentration data will be descriptively summarized using nominal times: number of observations (n), arithmetic mean (Mean), standard deviation (SD), standard error of the mean (SEM), coefficient of variation (CV%), minimum (Min), median (Median) and maximum (Max).

Descriptive statistics of PK concentration data will be calculated using values with the same precision as the source data, and rounded for reporting purposes only. The following conventions will be applied when reporting descriptive statistics of PK concentration data:

Mean, Min, Median, Max: 3 significant digits

SD, SEM 4 significant digits

CV%: 1 decimal place

Values below the lower limit of quantification of the assay (LLOQ) will be taken as zero for summary statistics of PK concentration data. For final evaluations values greater than the upper limit of quantification (ULOQ) are not accepted and should be replaced by valid numeric values

from dilution measurement. Missing concentrations (e.g. no sample, insufficient sample volume for analysis, no result or result not valid) will be reported and used generally as “N.R.”. Pre-dose samples that occur before the first drug administration will be assigned a time of 0 hours, as if the sample had been taken simultaneously with the study drug administration.

### **General Specifications for PK Parameter Data**

PK parameter data will be descriptively summarized: number of observations (n), Mean, SD, SEM, CV%, Min, Median, Max, geometric mean (GeoMean), the geometric coefficient of variation (GeoCV) and the 95% confidence interval for the GeoMean (LCI 95% GM, UCI 95% GM).

PK parameter  $C_{max}$  will be reported with the same precision as the source data. All other PK parameters will be reported to 3 significant figures. In export datasets, as well as in the SDTM PP domain, PK parameters will be provided with full precision, and will not be rounded. Descriptive statistics of PK parameter data will be calculated using full precision values, and rounded for reporting purposes only.

The following conventions will be applied when reporting descriptive statistics of PK parameter data:

Mean, Min, Median, Max, GeoMean, 95% CI: 3 significant digits

SD, SEM: 4 significant digits

CV%, GeoCV%: 1 decimal place

Ratio of GeoMean and 95% CI 4 decimal places

To ensure a reliable estimate of the extent of exposure,  $AUC_{extra}$  should be less than or equal to 20%. If  $AUC_{extra}$  is greater than 20%, all parameters derived using  $\lambda_z$  (ie,  $\lambda_z$ ,  $t_{1/2}$ ,  $AUC_{0-\infty}$ ,  $AUC_{extra}$ ,  $V_z/f$ ,  $CL/f$ ) will be listed, but set to missing for the calculation of descriptive statistics.

All statistical analyses and descriptive summaries of pharmacokinetic data will be performed on the PK Analysis Set. All available PK data will be listed. Data of subjects not in the PK analysis set or invalid data will be flagged accordingly.

In this phase 1 PK study missing observations will be assumed to be missing completely at random (MCAR). No action will be taken to handle missing data. A subject who withdraws prior to the last planned observation in a trial period will be included in the analyses up to the time of discontinuation.

#### **16.1.1 Primary Endpoints**

The effect of omeprazole co-administration on the single dose PK of tepotinib under fed conditions will be investigated by comparing treatments A and C.

A linear model with TREATMENT, PERIOD, SEQUENCE and SUBJECT(SEQUENCE) as fixed effects will be applied to log-transformed PK parameters  $C_{max}$ ,  $AUC_{0-t}$ , and  $AUC_{0-\infty}$  of tepotinib based on the PK analysis set. Treatment differences C-A on the log scale will be estimated for  $C_{max}$ ,  $AUC_{0-t}$ , and  $AUC_{0-\infty}$  together with their 90% CIs. Point estimates and CIs will be back-transformed to the original scale.

The primary endpoints will be descriptively summarized. Scatter plots will be produced for each primary endpoint by treatment group indicating the geometric means within each treatment group.

### **16.1.2 Secondary Endpoints**

The effect of food on the single dose PK of tepotinib after co-administration of omeprazole and tepotinib will be investigated by comparing treatments B and C using the linear model described above in 16.1.1, again applied to log-transformed  $C_{max}$ ,  $AUC_{0-t}$ , and  $AUC_{0-\infty}$  of tepotinib.  $C_{max}$ ,  $AUC_{0-t}$ , and  $AUC_{0-\infty}$  of tepotinib under treatment B will be summarized together with treatments A and C in one table. The scatterplots for treatment B will be included in the scatterplots produced for the primary endpoints (16.1.1)

The relative bioavailabilities C/B and C/A will be calculated for each subject and summarized.

Summary statistics will also be provided for  $t_{max}$ ,  $t_{1/2}$ ,  $t_{lag}$ ,  $CL/f$  and  $Vz/f$  of tepotinib (all treatments). For  $t_{max}$ , the Hodges-Lehmann shift estimates will be given for C-B and C-A together with the 90% confidence intervals according to Tukey. PK variables will be evaluated for all subjects of the PK population, but listed for all subjects with available data.

### **16.1.3 Exploratory Endpoints**

The effect of omeprazole co-administration on the PK of metabolites of tepotinib under fed conditions will be investigated.

A linear model with the same terms as for the primary analysis will be fitted for the log transformed exploratory PK parameters  $AUC_{0-t}$ ,  $AUC_{0-\infty}$ ,  $C_{max}$  for the metabolites. Treatments A and C will be compared.

The relative bioavailabilities C/A will be calculated for each subject and summarized.

Summary tables will be presented for PK parameters  $AUC_{0-t}$ ,  $AUC_{0-\infty}$ ,  $C_{max}$ ,  $t_{max}$ , and  $t_{1/2}$  based on tepotinib metabolites MSC2571109A and MSC2571107A.

Ratios of tepotinib metabolites to tepotinib:  $MR_{AUC_{0-\infty}}$  and  $MR_{C_{max}}$  will also be summarized descriptively.

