8.5.2 Analysis of Primary Endpoint

A linear model with TREATMENT, PERIOD, SEQUENCE and SUBJECT(SEQUENCE) as fixed effects will be applied to log-transformed PK parameters C_{max} , AUC_{0-t} , and $AUC_{0-\infty}$ based on the PK analysis set. Treatment differences C-A and C-B on the log scale will be estimated for C_{max} , AUC_{0-t} , and $AUC_{0-\infty}$ together with their 90% CIs. Point estimates and CIs will be back-transformed to the original scale.

The relative bioavailabilities C/A and C/B will be calculated for each subject and summarized.

Graphical displays will be given, where appropriate. Details of the statistical analysis will be described in the SAP.

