8.5.5 Analysis of Exploratory Endpoints

Summary statistics will be provided for all exploratory PK parameters as well as for the concentrations of the tepotinib and metabolites in plasma by time point. PK variables of tepotinib and the metabolites will be listed for all subjects with data. Graphical displays will be given, where appropriate. Further details of the statistical analysis will be described in the SAP.

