## Changes to the Planned Analyses in the Clinical Trial Protocol

The statistical methods as described in the protocol were adopted.

# 8

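### Does the metabolite comparison in SAP 16.1.3 need its estimate and confidence level spelled out?

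*SAP*

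**What the plan says.** SAP 16.1.3 covers the exploratory objective on metabolite PK under fed conditions. It states: "A linear model with the same terms as for the primary analysis will be fitted for the log transformed exploratory PK parameters" AUC0-t, AUC0-∞ and Cmax of the metabolites. The next sentence is "Treatments A and C will be compared". It adds a descriptive output, "The relative bioavailabilities C/A will be calculated for each subject and summarized", and then summary tables and metabolite-to-parent ratios.

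The corresponding text for tepotinib is fuller. SAP 16.1.1 estimates the C-A difference on the log scale "together with their 90% CIs. Point estimates and CIs will be back-transformed to the original scale". Protocol 8.5.2 says "Treatment differences C-A and C-B on the log scale will be estimated", also with 90% intervals.

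For exploratory endpoints, protocol 8.5.5 says "Summary statistics will be provided for all exploratory PK parameters", adds listings and graphs, and leaves further detail to the SAP. SAP section 7 says "The statistical methods as described in the protocol were adopted". Among the SAP's rounding conventions for PK parameter data is the line "Ratio of GeoMean and 95% CI 4 decimal places".

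**The concern.** Carrying over the model terms does not, read strictly, carry over what is reported from the model. SAP 16.1.3 gives no point estimate, interval, level or back-transformation. The protocol has no fallback, because it plans no model for the metabolites. The one place where the SAP attaches a level to a ratio of geometric means without naming a comparison says 95%. A programmer working from that line could produce 95% metabolite intervals beside 90% tepotinib intervals, and the two sets would be awkward to compare.

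The effect of omeprazole on the metabolites is a stated exploratory objective. Apart from the summarised individual C/A ratios, this model gives its only direct between-treatment estimate. It is therefore fair to ask whether the plan fixes the output.

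**Working it through.** **1. Which level do the documents use for treatment comparisons?**

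| Place | Comparison | Level |
|---|---|---|
| Protocol 8.1, Table 7 | test/reference ratio | 90% |
| Protocol 8.5.2 | C-A and C-B, tepotinib | 90% |
| SAP 16.1.1 | C-A, tepotinib | 90%, back-transformed |
| SAP 16.1.2 | C-B and C-A, tmax shift | 90% |
| SAP 16.1.2 | C-B, exposure parameters | not restated; protocol 8.5.2 gives 90% |
| SAP 16.1.3 | A versus C, metabolites | not stated |
| SAP 16.1, rounding line | none named | 95% |

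Every interval tied to a named comparison is at 90%. The 95% line stands in a list of reporting precision for descriptive statistics. It names no analyte, so it fits tepotinib as badly as it fits the metabolites and cannot be a metabolite rule.

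**2. Is the planned precision really at 90%?** Inputs from protocol 8.1: n = 12, two-sided alpha 0.10, probability 0.80 of achieving the half-width, CV 10%, 15% and 20%. With s = √ln(1+CV²) and 11 degrees of freedom,

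half-width = exp[ t(0.95; 11) × s × √(2/12) × √(χ²(0.80; 11)/11) ] − 1.

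This gives 8.80%, 13.44% and 18.23%, against 8.8%, 13.4% and 18.2% in Table 7. All twelve pairs of limits in the table also match to two decimals. The planned precision for ratios is therefore at the 90% level.

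**3. What would a 95% reading do to the metabolite interval?** Two subjects in each of six sequences over three periods give 36 observations. The model uses 1 (intercept) + 11 (sequence and subject within sequence) + 2 (period) + 2 (treatment) = 16 parameters, leaving 20 residual degrees of freedom. The standard error of C-A is s√(2/12). The ratio of log-scale widths is

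t(0.975; 20) / t(0.95; 20) = 2.086 / 1.725 = 1.21,

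so a 95% interval is 21% wider. The documents give no metabolite CV, so a range is assumed. Expected upper half-width = exp[s√(2/12) × t] − 1:

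| Assumed CV | 90% | 95% |
|---|---|---|
| 10% | 7.3% | 8.9% |
| 20% | 15.0% | 18.4% |
| 30% | 23.0% | 28.4% |

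For an observed ratio of 1.00 and CV 20%, the limits are 0.870 to 1.150 at 90% and 0.845 to 1.184 at 95%.

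**4. Can a reader move between the levels?** Yes, if the level is printed and the degrees of freedom are known. Take an observed ratio of 0.85 at CV 20%. The 90% log half-width is 0.1394, giving 0.739 to 0.977. Multiplying by 1.21 gives 0.1687, hence 0.718 to 1.006. The estimate stays at 0.85.

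**The case for a change.** The best argument for a change is that an analysis plan exists to fix such details before the data are seen. Protocol 8.5.5 passes the detail to the SAP, and the SAP does not supply it. The SAP's text on intervals for the primary comparison is confined to tepotinib. The example in step 4 also shows that, for some data, the level decides whether 1 lies inside the interval. The repair would be a sentence or two, with no protocol amendment and no new data.

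Part of this stands: the wording in 16.1.3 is incomplete, and the 95% in the rounding line does not agree with the 90% used for treatment comparisons. The rest carries little weight.

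- SAP 16.1.1 opens by describing its task as a comparison of A and C and then sets out what that comparison consists of. SAP 16.1.3 uses the same comparison, the same three log-transformed parameters and the same model, so an analyst would carry over the same output.
- The example depends on an assumed ratio and CV, and on a check against 1 that neither document makes. Protocol 8.1 describes the analysis as descriptive, without hypothesis tests, and no no-effect boundary is set for any analyte.
- Adding a model for an exploratory endpoint is the kind of detail that protocol 8.5.5 leaves to the SAP. An entry in SAP section 7 would be housekeeping; the addition does not conflict with the protocol.
- Simply replacing 95% by 90% in the rounding line is not clearly right, because the line could also refer to descriptive summaries of the individual ratios.

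**Conclusion.** The observation about the text is correct, but it does not call for a change. SAP 16.1.3 leaves a gap that an analyst would fill in the obvious way, with the C-A difference on the log scale, a 90% interval and back-transformation, as in 16.1.1. The 95% in the rounding line is probably a clerical slip and does not set 95% for the metabolites against 90% for tepotinib.

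If the other level were used, the cost would be an interval 21% wider on the log scale, with the same point estimate. That figure assumes 12 complete subjects and the full three-treatment model; the half-widths also rest on assumed CVs of 10% to 30%. The comparison is exploratory and descriptive, no decision depends on it, and an interval labelled with its level can be converted. No tepotinib result or conclusion is affected.

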### 16.1.4

### Plasma Concentration Data

Concentrations of tepotinib and its metabolites will be tabulated and displayed graphically. Summary statistics will be provided by treatment and nominal timepoint.

The following figures will be produced, separately for tepotinib, MSC2571109A and MSC2571107A:

- Arithmetic mean plasma concentration-time profiles overlaying all treatments on linear and semi-logarithmic scale
- Arithmetic mean plasma concentration-time profiles overlaying all treatments on linear scale including SD error bars
- Individual plasma concentration-time profiles overlaying subjects, for each treatment separately on linear and semi-logarithmic scale
- Individual plasma concentration-time profiles overlaying all treatments, separately for each subject on linear and semi-logarithmic scale

The following listing will be produced:

- Plasma concentrations will be listed for each analyte by treatment, subject, and nominal time. Excluded plasma concentrations will be flagged.

### 16.1.5

### Estimation of Individual Pharmacokinetic Parameters

The following non-compartmental PK parameters (see [Table 1](#)) will be calculated from the individual plasma total tepotinib its metabolites MSC2571109A and MSC2571107A concentration-time data using commercial software such as Phoenix®/WinNonlin® (Version 6.2 or higher) at Nuvisan GmbH.

**Table 1**

**Definition of PK Parameters for Tepotinib and Metabolites after Single Dose Administration**

Symbol	Definition
AUC 0-t	Area under the plasma concentration-time curve (AUC) from time zero (= dosing time) to the last sampling time ( $t_{last}$ ) at which the concentration is at or above the lower limit of quantification (LLOQ), calculated using the mixed log linear trapezoidal rule (ie linear up/log down)

Symbol	Definition
$AUC_{0-\infty}$	Area under the plasma concentration-time curve from time zero (= dosing time) extrapolated to infinity, calculated as $AUC_{0-t} + AUC_{\text{extra}}$ . $AUC_{\text{extra}}$ represents the extrapolated part of $AUC_{0-\infty}$ calculated by $C_{\text{lastpred}}/\lambda_z$ , where $C_{\text{lastpred}}$ is the predicted plasma concentration at the last sampling time point, calculated from the log-linear regression line for $\lambda_z$ determination at which the measured plasma concentration is at or above LLOQ
$C_{\text{max}}$	Maximum plasma concentration observed
$t_{\text{last}}$	The last sampling time at which the plasma concentration is at or above the lower limit of quantification
$t_{\text{max}}$	Time to reach the maximum observed plasma concentration
$t_{1/2}$	Terminal half-life, calculated as $\ln(2)/\lambda_z$
$\lambda_z$	Terminal rate constant determined from the terminal slope of the log-transformed plasma concentration curve using linear regression on terminal data points of the curve
$CL/f$	Apparent total body clearance of drug from plasma following extravascular administration, calculated as dose/ $AUC_{0-\infty}$ , only parent drug, will not be calculated for the metabolites
$V_z/f$	Apparent volume of distribution during the terminal phase following extravascular administration, only parent drug, will not be calculated for the metabolites
$AUC_{\text{extra}}$	The AUC from time $t_{\text{last}}$ extrapolated to infinity
$AUC_{\text{extra}\%}$	$AUC_{\text{extra}} / AUC_{0-\infty} \times 100$ .
$MR_{AUC_{0-\infty}}$	Metabolite $AUC_{0-\infty}$ to parent $AUC_{0-\infty}$ ratio
$MR_{C_{\text{max}}}$	Metabolite $C_{\text{max}}$ to parent $C_{\text{max}}$ ratio
$F_{\text{rel,C/A}}$	Relative bioavailability (Test versus Reference), defined as $AUC_{0-\infty,C}/AUC_{0-\infty,A}$ and $AUC_{0-\infty,B}/AUC_{0-\infty,A}$ , where $AUC_{0-\infty,C}$ is $AUC_{0-\infty}$ under co-administration of omeprazole under fed conditions, $AUC_{0-\infty,B}$ is $AUC_{0-\infty}$ under co-administration of omeprazole under fasted conditions and $AUC_{0-\infty,A}$ is $AUC_{0-\infty}$ for tepotinib alone und fed condition.
$F = \frac{AUC_{0-\infty \text{ test}}}{AUC_{0-\infty \text{ reference}}} * 100$	

Individual PK parameters will be calculated using actual sampling times. The predose sample will be considered as if it had been taken simultaneously with the administration of study drug. PK variables will be evaluated and listed for all subjects who provide sufficient concentration-time data.

Plasma concentrations below LLOQ before the last quantifiable data point will be taken as zero for calculating the AUC (ie embedded below the limit of quantitation values set to zero). Plasma concentrations below LLOQ after the last quantifiable data point will not be considered for the determination of  $\lambda_z$ .

The following PK parameters will be calculated for diagnostic purposes and listed, but will not be summarized:

- The time interval (h) of the log-linear regression ( $\lambda_{z\ low}$ ,  $\lambda_{z\ upp}$ ) to determine  $\lambda_z$ .
- Number of data points included in the log-linear regression analysis to determine  $\lambda_z$ .
- Goodness of fit statistic (Rsq) for calculation of  $\lambda_z$ .

The regression analysis should contain data from at least 3 different time points in the terminal phase consistent with the assessment of a straight line on the log-transformed scale. Phoenix WinNonlin best fit methodology will be used as standard. The last quantifiable concentration should always be included in the regression analysis, while the concentration at  $t_{max}$  and any <LLOQ concentrations that occur after the last quantifiable data point should not be used.

The coefficient of correlation ( $R^2$ ) should be  $\geq 0.8$  and the observation period over which the regression line is estimated should be at least twofold the resulting  $t_{1/2}$  itself. If these criteria are not met, then the corresponding values should be flagged in the listing displaying Individual Plasma Pharmacokinetic Diagnostic Parameters for Each Treatment. Any flags should be included in the study specific SDTM. Then the rate constants and all derived parameters (e.g.  $AUC_{0-\infty}$ , % $AUC_{extra}$ ,  $CL/f$ ,  $t_{1/2}$ , and  $Vz/f$ ) will be included in the parameter listings and will be discussed appropriately in alignment with the protocol lead and quantitative pharmacology representative.

Partial areas  $AUC_\tau$  should be calculated using the scheduled dosing interval, as defined in the Clinical Trial Protocol. The actual dosing interval calculated from eCRF time data should not be used. The following rules apply when calculating the partial area  $AUC_\tau$  within the observed time interval from  $T_1$  to  $T_2$ :

- If the start time of the interval ( $T_1$ ) occurs before the first observation, the observation at  $T_1$  will be estimated using the linear interpolant between the first datapoint and  $C_0$ . For single dose data  $C_0 = 0$  when the drug was administered via an extravascular route. For steady state models,  $C_0$  is the minimum concentration value occurring within the time interval  $T_1$  to  $T_2$ .
- If either  $T_1$  or  $T_2$  falls within the time range in which samples were taken, but does not coincide with an observed data point, then a linear or logarithmic interpolation is

performed to estimate the corresponding concentration value. Whether a linear or logarithmic interpolation is used will depend on the method of AUC calculation e.g. linear up log down.

- If the end time of the interval ( $T_2$ ) occurs after the last measurable concentration and the terminal regression ( $\lambda_z$ ) is estimable, then  $\lambda_z$  is used to estimate the concentration at time  $T_2$ . The log trapezoidal rule will be used to calculate the area from the last observation time to the end time of the partial area ( $T_2$ ). If  $\lambda_z$  cannot be estimated the partial area will not be calculated.

The IMP dose administered is given for the monohydrate hydrochloride salt (ie, 500 mg IMP). A conversion factor for the freebase IMP was calculated and will be applied when 'dose' is used in deriving PK parameter formulas needing a dose value (CL/f).

Conversion factor = Molecular weight (MW) of base IMP divided by MW of salt form IMP = 492.574 g/mol / 547.05 g/mol = 0.9004

Amount of dose \* conversion factor = actual dose of IMP: 500 mg \* 0.900 = 450 mg

The Phoenix WinNonlin NCA Core Output will be provided in a separate listing.

